9.1.1 Additional Safety Information

In addition to AEs, there are safety-related situations in which other information must be collected, regardless of whether or not there is an associated AE. These include:

- Use during pregnancy (i.e., drug exposure to a fetus in utero).
- Exposure to a drug during breast-feeding/lactation.

- Overdose (whether intentional, accidental or prescribed; whether symptomatic or not).
 - O An overdose is defined as the administration of a quantity of a medicinal product given per administration or cumulatively which is above the maximum recommended dose according to the authorized product information. When applying this definition, clinical judgment should always be applied.
- Drug abuse or misuse.
- Medication errors (including dispensing errors, accidental exposure, maladministration, etc.).
- Unapproved or off-label use (i.e., intentional medical use of a product not in conjunction with the authorized product information).
- Withdrawal reactions/rebound effects.
- Unusual exacerbation of existing disease.
- Suspected use of counterfeit/falsified medicines/tampering.
- Drug-drug/drug-food interactions.
- Occupational exposure (as a result of one's professional or non-professional occupation).
- Unexpected or unintended benefit/effect.
- Actual or potential transmission via a medicinal product of an infectious agent.

If these above events occur and are serious (see Section 9.2), they should be reported using the SAE Report Form within 24 hours by fax or email. If non-serious, the events should be reported in the eCRF.

9.1.2 Assessment of Adverse Events by the Investigator

The Investigator will assess the severity (intensity) of each AE as mild, moderate, or severe, and will also categorize each AE as to its potential relationship to avatrombopag using the categories of yes or no.

9.1.2.1 Severity Assessment

- Mild A type of AE that is usually transient and may require only minimal treatment or therapeutic intervention. The event does not generally interfere with usual activities of daily living.
- Moderate A type of AE that is usually alleviated with additional specific therapeutic intervention. The event interferes with usual activities of daily living, causing discomfort but poses no significant or permanent risk of harm to the research participant.
- Severe A type of AE that interrupts usual activities of daily living, or significantly affects clinical status, or may require intensive therapeutic intervention.

9.1.2.2 Causality Assessment

The relationship of an AE to the administration of avatrombopag is to be assessed according to the following definitions:

- No (unrelated, not related, no relation) The time course between the administration of avatrombopag and the occurrence or worsening of the AE rules out a causal relationship and another cause (concomitant drugs, therapies, complications, etc.) is suspected.
- Yes (related) The time course between the administration of avatrombopag and the occurrence or worsening of the AE is consistent with a causal relationship and no other cause (concomitant drugs, therapies, complications, etc.) can be identified.
 - The definition implies a reasonable possibility of a causal relationship between the event and avatrombopag. This means that there are facts (evidence) or arguments to suggest a causal relationship.

The following factors should also be considered:

- The temporal sequence from avatrombopag administration-
 - The event should occur after avatrombopag is given. The length of time from avatrombopag exposure to event should be evaluated in the clinical context of the event.
- Underlying, concomitant, intercurrent diseases-
 - Each report should be evaluated in the context of the natural history and course of the disease being treated and any other disease the subject may have.
- Concomitant drug(s)-
 - The other drugs the subject is taking or the treatment the subject receives should be examined to determine whether any of them might be recognized to cause the event in question.
- Known response pattern for this class of medication-
 - O Clinical and/or preclinical data may indicate whether a particular response is likely to be a class effect.
- Exposure to physical and/or mental stresses-
 - The exposure to stress might induce adverse changes in the subject and provide a logical and better explanation for the event.
- The pharmacology and PK of avatrombopag
 - o The known pharmacologic properties (absorption, distribution, metabolism, and excretion) of avatrombopag should be considered.

9.2 Serious Adverse Events

An AE or adverse reaction is considered serious if, in the view of either the Investigator or Sponsor, it results in any of the following outcomes:

- Death,
- A life-threatening AE,
 - NOTE: An AE or adverse reaction is considered "life-threatening" if, in view of either
 the Investigator or Sponsor, its occurrence places the subject at immediate risk of death.
 It does not include an event that, had it occurred in a more severe form, might have
 caused death.
- Requires hospitalization or prolongation of existing hospitalizations,
 - ONOTE: Any hospital admission will be considered an inpatient hospitalization, even if admitted and discharged on the same day. An emergency room visit without hospital admission will not be recorded as an SAE under this criterion, nor will hospitalization for a procedure scheduled or planned before signing of informed consent. However, unexpected complications and/or prolongation of hospitalization that occur during elective surgery should be recorded as AEs and assessed for seriousness. Admission to the hospital for social or situational reasons (i.e., no place to stay, live too far away to come for hospital visits) will not be considered inpatient hospitalizations. Hospitalization due to expected recovery time for the planned procedure will not be counted as an SAE.
- A persistent or significant disability/incapacity or substantial disruption of the ability to conduct normal life functions,
- A congenital anomaly/birth defect, or
- An important medical event.
 - ONOTE: Important medical events that may not result in death, be life-threatening, or require hospitalization may be considered an SAE when, based upon appropriate medical judgment, they may jeopardize the subject and may require medical or surgical intervention to prevent one of the outcomes listed above. Examples of such medical events include allergic bronchospasm requiring intensive treatment in an emergency room or at home, blood dyscrasias or convulsions that do not result in inpatient hospitalizations, or the development of drug dependency.

9.3 Method of Detecting Adverse Events and Serious Adverse Events

AEs will be reported by the subject (or, when appropriate, by a healthcare provider, caregiver or surrogate). Care will be taken not to introduce bias when detecting AEs and/or SAEs. Open-ended and non-leading verbal questioning of the subject is the preferred method to inquire about AE occurrences.

9.4 Serious Adverse Event Reporting – Procedures for Investigators

9.4.1 Initial Reports

All SAEs, regardless of causal assessment, occurring from the time of informed consent until discharge from the study at Day 90 must be reported to the Sponsor as directed on the SAE reporting form within 24 hours of the knowledge of the occurrence (this refers to any AE that meets any of the aforementioned serious criteria). All SAEs that the Investigator considers causally related to avatrombopag occurring after discharge from the study must be reported to the Sponsor.

To report the SAE, complete the appropriate form for the study and submit to the Sponsor or designee as instructed on the form. It is very important that the form be filled out as completely as possible at the time of the initial report. This includes the Investigator's assessment of causality. The Investigator must notify his/her Institutional Review Board (IRB) of the occurrence of the SAE, in writing, if required by their institution. A copy of this communication must be forwarded to the Sponsor to be filed in the Sponsor's Trial Master File.

After discharge from the study, if the Investigator becomes aware of an SAE which, per the Investigator, is attributable to avatrombopag treatment, the event should be reported to the Sponsor within 24 hours of awareness.

The detailed contact information for reporting of SAEs is provided in the Investigator Study File.

9.4.2 Follow-up Reports

The Investigator must continue to follow the subject until the SAE has subsided or until the condition becomes chronic in nature, stabilizes (in the case of persistent impairment), the subject is lost to follow-up, or the subject dies.

Any follow-up information received on SAEs should be forwarded within 1 business day of its receipt. If the follow-up information changes the Investigator's assessment of causality, this should also be noted on the appropriate SAE follow-up form. Preliminary SAE reports should be followed as soon as possible by detailed descriptions including copies of hospital case reports, autopsy reports, and other documents requested by the Sponsor.

Within 24 hours of receipt of follow-up information, the Investigator must update the appropriate form for the study and submit any supporting documentation (e.g., subject discharge summary or autopsy reports) via fax or e-mail.

9.5 Adverse Events of Special Interest

The Investigator will monitor each subject for clinical and laboratory evidence for pre-defined AESIs throughout their participation in this study. The purpose for specifying these AESI is to enable further characterization of the clinical course and management of these events. An AESI may or may not be the consequence of treatment with avatrombopag.

The AESIs defined in this protocol include:

- Thromboembolic events (any thrombotic or embolic event, whether arterial or venous)
- Bleeding events (any clinically significant blood loss [e.g., WHO Grade 2 or higher]).

These events will be recorded on the AE eCRF page. The Investigator will assess and record any additional information on the AESI in detail on a SAE form (whether or not the event meets seriousness criteria in Section 9.2), to be submitted within 24 hours of awareness of the event. During the course of the study, additional AESIs may be identified by the Sponsor.

9.6 Pregnancy Reporting

If a subject becomes pregnant during the study, the Investigator should report the pregnancy using the Pregnancy Report Form within 24 hours of being notified. Monitoring of the subject should continue until conclusion of the pregnancy, which may involve follow—up after the subject's involvement in the study has ended. Abnormal pregnancy outcomes (e.g., spontaneous abortion, fetal death, stillbirth, congenital anomalies, ectopic pregnancy) are considered SAEs.

9.7 Regulatory Reporting Requirements for Serious Adverse Events

Regulatory reporting requirements for SAEs include:

- Prompt notification by the Investigator to the Sponsor, or designee, of an SAE is essential so that legal obligations and ethical responsibilities towards the safety of subjects and the safety of a study intervention under clinical investigation are met.
- The Sponsor has a legal responsibility to notify both the local regulatory authority and other regulatory agencies about the safety of a study intervention under clinical investigation. The Sponsor, or designee, will comply with country-specific regulatory requirements relating to safety reporting to the regulatory authority, IRB, and Investigators.
- Investigator safety reports must be prepared for suspected unexpected serious adverse reactions (SUSARs) according to local regulatory requirements and Sponsor policy. These safety reports will be forwarded to Investigators as necessary.
- An Investigator who receives an Investigator safety report describing a SUSAR or other specific safety information (e.g., summary or listing of SUSARs) from the Sponsor will review the report, file it, and will notify the IRB, if appropriate, according to local requirements.

10 STATISTICS

This section outlines the statistical methodology used for the safety, platelet count, and TSQM assessments. The detailed analyses will be provided in the Statistical Analysis Plan that will be finalized before the database lock.

10.1 Analysis Populations

The analyses and summaries of demographic and Baseline characteristics, safety assessments, and subject reported outcomes will be provided for the All Enrolled Population which is defined as all subjects who receive at least 1 dose of study drug.

10.2 Statistical Methods

10.2.1 Analysis of Safety

AEs, SAEs, and AESIs will be summarized for all enrolled subjects using counts and percentages. Treatment-emergent AEs and SAEs will be summarized overall, by system organ class, and by preferred term. AESIs will be summarized by event type (thromboembolic events and bleeding events). In addition, treatment-emergent AEs will be summarized by severity and by relationship to study drug.

Bleeding events reported during the study will be summarized by WHO grade.

10.2.2 Analysis of Platelet Count

Platelet count assessed at Baseline, Day 15, Day 30, Day 60, and Day 90 will be summarized descriptively for all enrolled subjects. Graphic presentations of platelet count over time will be provided.

The proportion of subjects who have a platelet count $\geq 50 \times 10^9 / L$ and $\leq 200 \times 10^9 / L$ will be tabulated using count and percentage for Baseline, Day 15, Day 30, Day 60, and Day 90.

10.2.3 Analysis of the Treatment Satisfaction Questionnaire for Medication

Domain scores of effectiveness, side effects, convenience, and global satisfaction will be computed according to the TSQM manual, Version 1.4. Each domain score ranges from 0 to 100, and a higher score indicates a better outcome. Descriptive statistics will be summarized for each domain score and each visit. The change from Baseline and percent change in each mean domain score will be summarized descriptively.

The primary interest in the TSQM assessment is the convenience domain score. The hypothesis is that switching from a prior TPO-RA treatment (e.g., eltrombopag or romiplostim) to avatrombopag results in an improvement in the convenience domain score. Change from Baseline to Day 90 (or End of Study) in the convenience domain score will be tested using paired t-tests, by prior TPO-RA treatment (eltrombopag vs romiplostim) and overall.

Additional analyses on platelet count and TSQM may be conducted as appropriate.

10.2.4 Sample Size Determination

The primary interest in assessing the TSQM in this study is the convenience domain score. An observational, retrospective study conducted in 2011 and supported by GlaxoSmithKline showed that the mean convenience score for eltrombopag-treated and romiplostim-treated subjects were 76.11 and 62.12, respectively. Study E5501-G000-302, a 6-month, randomized, placebo-controlled study in chronic ITP patients, showed that the mean TSQM convenience score assessed at Week 12 and at the End of Study for avatrombopag-treated patients was approximately 85 with a standard deviation (SD) which ranged from 12.2 – 14.8. Likewise, E5501-G000-305, a 6-month, randomized, active-control study in chronic ITP patients, showed that the mean TSQM convenience score assessed at the End of Study was 78.9 (SD = 15.4) for avatrombopag-treated patients and 68.2 (SD = 21.0) for eltrombopag-treated patients.

Assuming a mean TSQM convenience score at Baseline and at the End of Study of 74 and 82, respectively, with a SD of 19, 50 subjects will provide 83% power to detect a change from Baseline of 8 at a 2-sided significance level of 0.05 based on a paired t-test. The total sample size will be 100 subjects; approximately 50 subjects who received prior treatment with eltrombopag and approximately 50 subjects who received prior treatment with romiplostim.

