The purpose of this Phase 4 prospective study is to evaluate safety, platelet count, and subject reported treatment satisfaction after receiving avatrombopag for 90 days following treatment with either eltrombopag or romiplostim. The initial dose and dose adjustments of avatrombopag will be determined by the Investigator, per the DOPTELET USPI. There is no protocol-required washout period between treatment with TPO-RAs, however avatrombopag should not be administered on the same day as another TPO-RA. The start and stop dates of all prior and concomitant medications should be recorded in the electronic case report form (eCRF).

The Treatment Satisfaction Questionnaire for Medication (TSQM) Version 1.4 is a validated 14-item questionnaire designed as a general measure of treatment satisfaction with medication. In order to capture subject reported outcomes after switching from eltrombopag or romiplostim to avatrombopag, the TSQM will be administered at Baseline (before the first dose of avatrombopag), Day 30, and Day 90.

STUDY OBJECTIVES:

Primary Objective: Characterize the safety and tolerability of avatrombopag given for 90 days after stopping treatment with eltrombopag or romiplostim.

Secondary Objectives:

- Evaluate the change in subject reported outcomes from Baseline after switching to avatrombopag from eltrombopag or romiplostim.
- Evaluate the platelet counts after switching to avatrombopag from eltrombopag or romiplostim.

STUDY ENDPOINTS:

Primary Endpoint: Occurrence of adverse events (AEs) and serious adverse events (SAEs).

Secondary Endpoints:

- Change from Baseline in each of the 4 domains of the TSQM Version 1.4 (e.g., convenience, global satisfaction, effectiveness, and side effects) to Day 90 or End of Study.
- Proportion of subjects who have a platelet count between $\geq 50 \times 10^9 / L$ to $\leq 200 \times 10^9 / L$ at Day 15, Day 30, Day 60, and Day 90.

STUDY DESIGN AND DURATION: This Phase 4, prospective, multi-center, open-label study will evaluate safety, platelet count, and subject reported medication satisfaction in adult subjects with chronic ITP after switching to avatrombopag from eltrombopag or romiplostim. At least 100 subjects will be enrolled, 50 (±10) who have received eltrombopag and 50 (±10) who have received romiplostim for at least 90 days prior to study entry.

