Descriptive statistics will be summarized for each domain score and each visit. The change from Baseline and percent change in each mean domain score will also be summarized descriptively.

The primary interest in the TSQM assessment is the convenience domain score. The hypothesis is that switching from a prior TPO-RA treatment (eltrombopag or romiplostim) to avatrombopag results in an improvement in the convenience domain score. Change from Baseline to Day 90 (or End of Study) in the convenience domain score will be tested using paired t-tests, by prior TPO-RA treatment (eltrombopag vs romiplostim) and overall.

SAMPLE SIZE DETERMINATION:

Assuming the mean TSQM convenience scores at Baseline and at the end of study are 74 and 82, respectively, with a standard deviation (SD) of 19, 50 subjects will provide 83% power to detect a change from Baseline of 8 at a 2-sided significance level of 0.05 based on a paired t-test. The total sample size will be 100 subjects which includes approximately 50 subjects with a prior treatment of eltrombopag and approximately 50 subjects with a prior treatment of romiplostim.

SITES: Approximately 20 centers in the US.

SPONSOR:

Sobi, Inc. (Sobi)

[name] United States

TABLE OF CONTENTS

Tit	le Pag	e	Ĺ
Sig	nature	Page	2
Inv	estiga	tor Agreement	3
Syı	nopsis	4	ļ
Tal	ole of	Contents 9)
Lis	t of Ta	ables12	2
Lis	t of Fi	gures12	2
Lis	t of A	bbreviations and Definition of Terms	3
1	Introd	luction and Background Information	1
	1.1	Thrombocytopenia	1
	1.2	Immune Thrombocytopenia	ļ
	1.3	Avatrombopag	5
	1.4	Study Rationale	5
2	Study	Objectives	7
	2.1	Primary Objective	7
	2.2	Secondary Objectives 17	7
3	Study	Endpoints 18	3
	3.1	Primary Endpoint	3
	3.2	Secondary Endpoints	3
4	Study	Description)
	4.1	Summary of Study Design)
5	Selec	tion and Early Termination of Subjects)
	5.1	Inclusion Criteria)
	5.2	Exclusion Criteria 20)
	5.3	Subject and Study Discontinuation)
		5.3.1 Screen Failures	l
		5.3.2 Early Termination	l
6	Study	Treatment 22	2
	6.1	Randomization and Blinding	2
	6.2	Avatrombopag Supplies	2

	6.3	Avatrombopag Dosage and Administration	22
	6.4	Receipt of Supplies.	22
	6.5	Avatrombopag Storage Conditions	22
	6.6	Compliance	22
	6.7	Avatrombopag Accountability	23
	6.8	Avatrombopag Handling and Returns	23
7	Stud	y Procedures	24
	7.1	Informed Consent	24
	7.2	Screening Visit (Visit 1)	24
	7.3	Baseline Visit (Visit 2/Day 1)	25
	7.4	Treatment Period (through Day 90)	26

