4 STUDY DESCRIPTION

4.1 Summary of Study Design

This Phase 4, prospective, multi-center, open-label study will evaluate safety, platelet count, and subject reported medication satisfaction in adult subjects with chronic ITP after switching to avatrombopag from eltrombopag or romiplostim. At least 100 subjects will be enrolled, 50 (\pm 10) who have received eltrombopag and 50 (\pm 10) who have received romiplostim for at least 90 days prior to study entry. An overview of the study design is provided in Figure 1.

The initial dose and dose adjustments of avatrombopag will be determined by the Investigator in conjunction with the DOPTELET USPI. There is no protocol-required washout period between treatment with TPO-RAs, however avatrombopag should not be administered on the same day as another TPO-RA. The start and stop dates of all prior and concomitant medications should be recorded in the eCRF.

Safety will be evaluated throughout the study. Platelet counts will be collected per protocol at Baseline, Day 15, Day 30, Day 60, and Day 90, however, all other platelet counts collected per the subject's standard of care while they are enrolled in the study should be recorded in the eCRF. The TSQM will be administered prior to the first dose of avatrombopag (at Baseline), at Day 30, and at Day 90 or at the time of early termination from the study. Compliance with the Investigator prescribed avatrombopag dosing regimen will be captured via a subject reported Dosing Diary which should be evaluated by the study team during each visit to the clinic, per the subject's standard of care.

Subjects may be screened within 28 days of the Baseline Visit/Visit 2, however, the Screening Visit/Visit 1 may be combined with the Baseline Visit/Visit 2. The duration of subject participation and collection of clinical data will be a minimum of 90 days from the Screening Visit/Visit 1 to Day 90. The only protocol-required clinic visits during the study are the Baseline Visit/Visit 2, Day 15, Day 30, Day 60, and the Day 90 or Early Termination Visit.

If a subject is early terminated, the early termination assessments should be completed prior to discharge from the study.

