5 SELECTION AND EARLY TERMINATION OF SUBJECTS

5.1 Inclusion Criteria

Subjects who meet all of the following criteria will be eligible to participate:

- 1. Subject is willing and able to provide written informed consent.
- 2. Male or female aged ≥ 18 years of age at the Screening Visit/Visit 1.
- 3. Subject has been undergoing treatment for primary ITP with eltrombopag or romiplostim for at least 90 days prior to the Screening Visit/Visit 1.
- 4. Subject has had a previous response (at any time) to either eltrombopag or romiplostim, defined as at least 2 platelet counts $\geq 50 \times 10^9 / L$.
- 5. Subject is willing and able to comply with all aspects of the protocol, including completing the self-administered TSQM.

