5.3 Subject and Study Discontinuation

A subject can withdraw from the study, at any time, and for any reason. The standard of care for the subject will not be affected in any way.

If a subject withdraws prematurely from the study, study staff should make every effort to collect the full panel of data scheduled for the Day 90/Early Termination Visit.

The reason for early termination must be documented in the eCRF. Terminated subjects will not be replaced.

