5.3.2 Early Termination

A subject may be early terminated for any of the following reasons:

- Subject wishes to withdraw consent for any reason.
- Subject non-compliance or unwillingness to comply with the procedures required by the protocol.
- Subject failed to meet inclusion/exclusion criterion.
- Occurrence of any medical condition that exposes the subject to substantial risk and/or does not allow the subject to adhere to the requirements of the protocol.
- Any SAE, clinically significant AE, severe laboratory abnormality, intercurrent illness, or other medical condition which indicates to the Investigator that continued participation in the study is not in the best interest of the subject.
- Investigator discretion.
- Sponsor request.
- Termination of the study by the Sponsor or a regulatory agency.

If a subject is early terminated from the study, the Early Termination procedures (Section 7.4.5) should be performed. Subjects early terminated from the study will not be replaced, regardless of the reason for early termination.

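### Is the 83% power misleading because a prior-treatment group may be as small as 40 and the SD of 19 is not labelled?

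*Protocol*

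**What the plan says.** Protocol 10.2.4 takes mean convenience scores of 74 at Baseline and 82 at End of Study and states that, "with a SD of 19, 50 subjects will provide 83% power to detect a change from Baseline of 8", using a paired t-test at a two-sided level of 0.05. The Synopsis repeats this ("with a standard deviation (SD) of 19, 50 subjects will provide 83% power to detect a change from Baseline of 8"), as does SAP 3.4. The total of 100 is described as roughly 50 from each prior treatment.

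The SDs cited in support are all for scores, not changes. For example, the End of Study score in study E5501-G000-305 "was 78.9 (SD = 15.4) for avatrombopag-treated patients and 68.2 (SD = 21.0) for eltrombopag-treated patients".

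On group size, the Synopsis and Protocol 4.1 say: "At least 100 subjects will be enrolled, 50 (±10) who have received eltrombopag and 50 (±10) who have received romiplostim". Protocol 10.2.3 and SAP 8.1 run the paired test within each prior-treatment group and overall.

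On missing pairs, Protocol 5.3.2 says: "Subjects early terminated from the study will not be replaced, regardless of the reason for early termination". SAP 4.3.4 plans no imputation for study endpoints. On the other side, the TSQM is given "at Day 30, and at Day 90 or at the time of early termination from the study" (Protocol 4.1), Protocol 5.3 says that "study staff should make every effort to collect the full panel of data scheduled for the Day 90/Early Termination Visit", and an entry criterion in Protocol 5.1 reads: "Subject is willing and able to comply with all aspects of the protocol, including completing the self-administered TSQM".

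**The concern.** A paired t-test draws its power from the number of complete pairs and the SD of the within-subject change, and the power statement looks loose on both.

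First, 83% is given for 50 subjects, but the enrolment rule allows 40 to 60 in a group. Dropouts are not replaced, endpoints are not imputed, and no allowance is made for a missing Baseline or final score. A group can therefore fall short of 50 pairs while the plan is followed exactly.

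Second, 19 is attached to two visit means, and every SD quoted as background belongs to a score at one time point. No within-subject correlation is given. A reader cannot tell from the wording whether 19 already describes the change.

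Convenience is the TSQM domain of main interest and carries the only power calculation in the documents. A non-significant result in a smaller group might be read against 83% when the true figure was nearer 70%.

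**Working it through.** **Inputs.** Change 8 (82 − 74), SD 19, two-sided 0.05, paired t-test, 50 subjects (Protocol 10.2.4). Groups of 40 to 60 and at least 100 in total (Protocol 4.1). No missing-pair rate and no correlation are given, so both are varied below as assumptions.

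**Formula.** Power is the probability that a noncentral t variable, with n − 1 degrees of freedom and noncentrality (8/SD)·√n, exceeds the two-sided 5% critical value in absolute size.

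**1. The plan's own figure.** With SD of change 19 and n = 50, noncentrality is (8/19) × √50 = 0.421 × 7.071 = 2.98, and power is 83.1%. The stated 83% reproduces. The normal approximation gives 84.6%, so the 83% agrees with the exact t calculation.

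**2. Group size and missing pairs.** SD of change 19; number of pairs in brackets, rounded down.

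| Enrolled in group | All pairs complete | 5% missing | 10% missing | 15% missing |
|---|---|---|---|---|
| 40 | 73.8% | 71.5% (38) | 69.0% (36) | 66.4% (34) |
| 50 | 83.1% | 80.7% (47) | 78.9% (45) | 75.9% (42) |
| 60 | 89.4% | 87.8% (57) | 85.9% (54) | 83.9% (51) |

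The overall test has 98.6% at 100 pairs and 97.7% at 90. Because the total is at least 100 and no group may exceed 60, a group of 40 forces the other to 100 − 40 = 60. Only one row for 40 can occur in the trial, and it comes with the row for 60.

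In points on the 0 to 100 scale, the change detectable with 80% power is 7.68 at 50 pairs and 8.63 at 40, a difference of 0.95.

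**3. What 19 could be.** If 19 were the SD at each visit, the SD of the change would be 19 × √(2(1 − r)), with r the assumed correlation between visits.

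| r | SD of change | n = 40 | n = 50 | n = 60 |
|---|---|---|---|---|
| 0.3 | 22.48 | 59% | 69% | 77% |
| 0.5 | 19.00 | 74% | 83% | 89% |
| 0.7 | 14.72 | 92% | 96% | 99% |

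At r = 0.5 the two readings coincide, so the match at 83% does not by itself say which was meant. The cited SDs of 15.4 and 21.0, combined at r = 0.5, give √(21.0² + 15.4² − 2 × 0.5 × 21.0 × 15.4) = √354.76 = 18.8, which rounds to 19. Their equal-weight pooled single-visit value is √((21.0² + 15.4²)/2) = 18.4. This leans towards 19 as the SD of the change without proving it.

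**4. Sensitivity to the true change.** Everything above assumes a change of exactly 8. At 78.9 − 68.2 = 10.7, the difference between arms in study E5501-G000-305, 40 pairs have 93.5%. For prior romiplostim, the cited means differ by 78.9 − 62.12 = 16.8, where 40 pairs exceed 99.9%. For prior eltrombopag, one cited comparison is only 78.9 − 76.11 = 2.8, where power would be low at 40 or at 50. The last two are cross-study differences and serve only to show how widely the effect could vary.

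**The case for a change.** The best case for acting is that the correction costs almost nothing. An unlabelled SD is a real gap in a paired calculation: only the sponsor can say what 19 is, and one phrase would settle it. The 83% is also fragile. Power of 80% needs 47 pairs, so a group of exactly 50 drops below it after losing four. Giving power for 40, 50 and 60 would let a reader judge a null result in one group fairly.

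Part of this stands. The label is missing, and no power is given for the ends of the permitted range. The rest is weaker. The text claims 83% for 50 subjects and claims nothing for 40. The 69% depends on a 10% loss that no document supplies, while the plan takes several steps to keep loss small: a TSQM at early termination, recorded at the same visit as Day 90; an endpoint defined as Day 90 or End of Study; and a convenience score that is still computed with one item missing (SAP 8.1). On the SD, the natural reading for a paired t-test is the SD of the differences, and that reading reproduces the stated power.

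**Conclusion.** No change follows. The stated power is correct for the case it describes. At the edge of the permitted enrolment it falls by about nine percentage points (83.1% to 73.8%) in one group, while the other rises to 89.4% and the overall test stays near 99%. These values assume that 19 is the SD of the change, that the true change is 8 and that all pairs are complete. The lower values need an assumed loss of pairs or an assumed correlation below 0.5; a correlation above 0.5 would raise power instead.

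The consequence is slight. Safety is the primary endpoint, the TSQM is secondary, and no decision rule in either document rests on this power. The planned tables show the number of non-missing values, the mean and the SD by prior treatment and overall (SAP 4.3.1, 4.4), so a reader will see the actual group sizes and the observed SDs. Once the data are in, the paired tests, estimates and p-values are the same whatever the sample size section says. What is left is a missing label and an absent sensitivity table: details that might help a reader but would gain nothing in the analysis.
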